2.5 Number of Subjects and Duration of Study

The total planned number of subjects is approximately 210. Approximately 210 subjects will be randomly assigned to receive 1 of the 2 active treatments or placebo (70 subjects in each group); subjects will be randomized using a 1:1:1 ratio.

The expected participation period for a subject is approximately 26 weeks, including a pretreatment phase consisting of a Screening visit followed by a 7- to up to 21-day single-blind- placebo run-in period and a 24-week double-blind treatment phase.

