9.1 Sample Size Determination

Sample size assumptions were originally generated based on previous Phase 3 studies of OPN-375 in subjects with nasal polyposis and data from a study evaluating the change in maxillary and ethmoid opacification in CRS patients treated with an intramuscular dose of triamcinolone (Pallanch 2013). Updated standard deviation estimates for both co-primary endpoints in this amendment are based on a blinded interim analysis of Protocol OPN-FLU-CS-3205. Based on the results for changes from baseline in morning symptoms among subjects with nasal polyps in the previous studies conducted with OPN-375, a sample of 70 subjects per group (210 total subjects) is sufficient to detect a 0.9 scale difference in 7-day average CSNS (AM instantaneous) between treatments (OPN-375 vs placebo) using a 2-sided test at the 5% significance level with 88% power, and assuming a standard deviation (SD) of 1.7. This sample size is also adequate to detect a 9% difference between treatments in average percent opacification (APOV) using a 2-sided test at the 5% significance level with 88% power, and assuming a SD of 17%. The sample size was estimated for the co-primary efficacy endpoints using Power Analysis and Sample Size Software (PASS 15) (NCSS, 2017).

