9.5 Key Secondary Efficacy Analyses

The analysis of the following key secondary endpoints are based on pooling the data from Study OPN-FLU-CS-3205 and Study OPN-FLU-CS-3206 (pooled data):

- Change from baseline to Week 4 on CSNS score in subjects who were symptomatic at trial entry despite reported use of an intranasal steroid for treatment of CRS within 30 days of Visit 1 will be analyzed using the same MMRM model described for the co-primary endpoint CSNS and the model will include a categorical effect term for protocol (CS-3205, CS-3206).
- The frequency of acute sinus exacerbations over 24 weeks will be compared between OPN-375 dose groups and placebo using generalized linear model (GLM) for data from the negative binomial distribution that is commonly referred to as the negative binomial (NB) regression model. The NB model will include the same model terms as the primary models; in addition, the model will include a categorical effect for protocol (OPN-FLU-CS-3205, OPN-FLU-CS-3206), and the logarithm of follow-up time as an offset variable. The same model will be used for the pooled analysis of the frequency of acute sinus exacerbations over 24 weeks in the CRS without Nasal Polyps population.

The analysis of the following key secondary endpoints are based on the data from Study OPN-FLU-CS-3206 only:

- change from baseline to the end of Week 4 in four separate cardinal CRS symptoms, as measured by (AM, Instantaneous) CSNS: congestion, facial pain or pressure sensation, nasal discharge (anterior and/or posterior), and sense of smell will be analyzed using the same MMRM model described above.
- The Kaplan-Meier method and log-rank test will be used to estimate and compare the distributions of time to first acute CRS exacerbation between each OPN-375 dose and placebo.

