9.6 Other Secondary Efficacy Analyses

All statistical analyses in this section that reference the primary MMRM and ANCOVA models described in Section 9.3.4 will include the same factors as their respective primary models, except for the baseline covariate. The baseline covariate for the specific endpoint will be used, unless otherwise specified.

In addition, a combined dose group (OPN-375 186 µg, OPN-375 372 µg) is defined in all models of primary and secondary endpoints by including appropriate model contrasts, assigning equal weight to each dose, to obtain the inferential statistics for combined doses, and for the comparison: combined dose versus placebo.

Intercurrent events for secondary endpoints will be addressed as described in Section 9.3.3 for the primary estimand, unless otherwise indicated, and poor scores assigned to secondary endpoints are defined in the SAP. For the treatment policy estimand, missing data due to study discontinuation will be handled as described in Section 9.3.4 for the primary MMRM and ANCOVA models, respectively.

The following secondary endpoints will be analyzed with MMRM models; further details will be provided in the SAP:

- Change from baseline in average instantaneous and reflective AM and PM CSNS and symptom scores (facial pain or pressure sensation, nasal discharge, sense of smell, and nasal congestion) – (except AM, instantaneous symptom scores – key secondary endpoints)
- Change from baseline SNOT-22 total scores and sub-domain scores
- Change from baseline to Week 24/ET in SNOT-22 total score in subjects from pooling studies OPN-FLU-CS-3205 and OPN-FLU-CS-3206 who report using an intranasal, topically acting nasal steroid for the treatment of CRS within 30 days of Visit 1
- Change from baseline to Week 24/ET PSQI global and component scores
- Change from baseline to Week 24/ET the Global PSQI Score from pooling studies OPN-FLU-CS-3205 and OPN-FLU-CS-3206
- Change from baseline to Week 4, 8, 12, and 24/ET in HPQ endpoints
 - number and percentage of missing work days over the past 4 weeks
 - percentage of productive work hours lost over the past 4 weeks

The following secondary endpoints will be analyzed using an ANCOVA model; further details will be provided in the SAP. Change from baseline to Week 24/ET:

- Lund-Mackay Staging System total score, scores for ethmoids and maxillary sinuses combined, and scores for each sinus pair (e.g., ethmoids, maxillary, frontal, sphenoid, and ostiomeatal complex),

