5 STATISTICAL METHODS FOR EFFICACY ANALYSES

5.1 Adjustments to the Statistical Models

In Protocol OPN-FLU-CS-3205 randomization was stratified by Nasal Polyp status at baseline (Absent, Present), and Prior Nasal Surgery (Yes, No). All statistical models in the OPN-FLU-CS-3205 SAP include categorical terms for both Nasal Polyp status and Prior Nasal Surgery.

In Protocol OPN-FLU-CS-3206 randomization was stratified only by Prior Nasal Surgery (Yes, No) since the subject population consisted only of subjects without Nasal Polyps at baseline. Therefore, for all statistical models referenced in OPN-FLU-CS-3205 SAP the categorical term for Nasal Polyp status is removed for the analyses of the efficacy endpoints in Protocol OPN-FLU-CS-3206.

There are no other changes to the statistical models or methods in the efficacy analyses of Protocol OPN-FLU-CS-3206.

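### As written in the protocol, two pooled 3205+3206 key secondary models omit nasal polyp status, a 3205 stratification factor, and the pooled SNOT-22 and PSQI models name no study term; the precision at stake is zero to small

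*Protocol*

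**What the plan says.** Protocol 9.5 defines two pooled key secondary models by reference to the primary models. For exacerbation frequency, "The NB model will include the same model terms as the primary models; in addition, the model will include a categorical effect for protocol", with log follow-up time as the offset. For CSNS in subjects symptomatic despite prior intranasal steroid, it uses the primary MMRM plus a protocol effect. In Protocol 9.3.4 the primary models adjust for previous sinus surgery and the baseline value (with week terms in the MMRM). Polyp status is not among the terms.

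In Protocol 9.8.2 these models serve steps 1 and 10 (exacerbations) and steps 3 and 12 (CSNS). SAP 5.3.2 numbers each of these one higher.

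SAP 5.1 records the difference between the studies: "In Protocol OPN-FLU-CS-3205 randomization was stratified by Nasal Polyp status at baseline (Absent, Present), and Prior Nasal Surgery (Yes, No". It adds that every 3205 SAP model carries both factors. Because 3206 has no subjects with polyps, "the categorical term for Nasal Polyp status is removed for the analyses of the efficacy endpoints in Protocol OPN-FLU-CS-3206". SAP 4.2 puts the 3206 stratification factor in the analysis model.

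For other secondary endpoints, Protocol 9.6 says that analyses based on the primary models "will include the same factors as their respective primary models, except for the baseline covariate". Pooled SNOT-22 and pooled PSQI fall under this rule, and no study effect is named for them.

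SAP 5.2 says the pooled endpoints will be fully described in the ISE SAP.

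**The concern.** A factor used to stratify randomisation normally belongs in the analysis model. If it is prognostic and left out, the model still counts the variation it explains as error, although the randomisation has already balanced it. The model-based standard error is then a little too large and the test a little conservative.

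The reason for dropping polyp status, that 3206 has only one level of it, does not carry over to pooled data containing 3205 subjects with polyps. A study effect separates 3205 from 3206, but polyp status varies within 3205.

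The place in the hierarchy is what makes this worth settling. Pooled exacerbation frequency at 372 µg is the first key secondary test and pooled CSNS is the third. Steps 4-9 in Protocol 9.8.2 are reached only if steps 1-3 succeed. The covariates of a gatekeeping model should not be open to two readings.

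**Working it through.** **1. The plan's own figure.** Protocol 9.1 powers the co-primaries, not the pooled tests: "a sample of 70 subjects per group (210 total subjects) is sufficient to detect a 0.9 scale difference in 7-day average CSNS (AM instantaneous"), "using a 2-sided test at the 5% significance level with 88% power, and assuming a standard deviation (SD) of 1.7". The normal approximation gives 0.9 / (1.7 × √(2/70)) = 3.132, and Φ(3.132 − 1.960) = 87.9%. The noncentral t with 138 df gives 87.5%. APOV (9% difference, SD 17%) has the same ratio and the same result. The stated 88% reproduces. No power is stated for any pooled test.

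**2. Inputs the documents do not give.** These are the size of 3205, its polyp share, exacerbation rates, dispersion, and the prognostic strength of polyps or study. All values below are assumptions.

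**3. Pooled CSNS (linear model with a study term).** Let w be the 3205 share of the pool, p the polyp share in 3205, and d the polyp difference in CSNS change. Adding the polyp term cuts residual variance by w·p(1−p)·d² / 1.7². Take p = 0.5 and w = 0.5-0.6, and let a test without the term have 80% power. Power with the term is Φ(2.802/√(1 − cut) − 1.960).

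| d (points) | variance cut | power with term |
|---|---|---|
| 0 | 0 | 80% |
| 0.5 | 1.1-1.3% | 80.4-80.5% |
| 1.0 | 4.3-5.2% | 81.7-82.1% |
| 1.5 | 9.7-11.7% | 83.9-84.6% |

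The last two rows need a polyp effect larger than the 0.9-point treatment effect the trial is powered for. In residual-SD units, with 210-300 subjects in 3205 and 30-50% polyps, the excess variance from omission is 0.7-0.9% for a 0.25 SD difference and 2.6-3.7% for 0.5 SD.

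**4. Pooled exacerbations (negative binomial).** Both simulations use about 600 replicates per scenario and fit the model with and without the polyp term.

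Set A assumes 300 subjects in 3205 and 210 in 3206, 40% polyps in 3205, 0.3 events per 24 weeks, dispersion 1 and treatment rate ratio 0.55.

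| polyp rate ratio | mean SE with | mean SE without | excess | power with / without |
|---|---|---|---|---|
| 1 | 0.2537 | 0.2539 | 0.1% | 68.7 / 68.8% |
| 1.5 | 0.2416 | 0.2425 | 0.4% | 70.4 / 70.4% |
| 2 | 0.2333 | 0.2357 | 1.0% | 75.7 / 74.7% |
| 3 | 0.2221 | 0.2287 | 3.0% | 76.5 / 74.7% |

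Set B assumes 70 or 110 per arm in 3205, 70 per arm in 3206, 50% polyps in 3205, 0.35 events per 24 weeks on placebo without polyps, dispersion 0.5 and treatment rate ratio 0.6. Power gains for polyp rate ratios 1.5, 2 and 3 were 0.5, 0.6 and 2.6 points at 70 per arm, and 0.0, 1.5 and 2.3 points at 110 per arm. About 0.5-6% of replicates gave no usable fit and were dropped.

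The Monte Carlo error of one power estimate near 75% is √(0.75 × 0.25 / 600) = 1.8 points. The comparison is paired, so the differences are steadier than that, but gains of 1-2 points remain rough.

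**5. Type I error.** With no treatment effect in Set A, rejection rates for polyp rate ratios 1, 1.5, 2 and 3 were 6.0, 5.2, 3.5 and 4.8% without the term, against 6.0, 5.0, 4.0 and 5.8% with it. The Monte Carlo error is √(0.05 × 0.95 / 600) = 0.9 points. Nothing suggests inflation from omitting the term.

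**6. Missing study term (pooled SNOT-22, PSQI).** Excess variance is w(1−w)·s², with s the between-study shift in residual SDs. At w = 0.5 this is 0.25% for s = 0.1, 1.0% for s = 0.2 and 2.25% for s = 0.3.

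**7. Which analyses are affected.** Pooled exacerbation frequency in the no-polyp population (steps 2 and 11) has only one polyp level, so no polyp term is needed. For pooled SNOT-22 and PSQI the sections disagree: Protocol 3.2.1.3 restricts both to CRS without polyps, while 2.3 and 9.6 state no such limit.

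**The case against.** The strongest objection is that the pooled models are not settled here. Protocol section 9 describes itself as principles, and SAP 5.2 hands the pooled endpoints to the ISE SAP. SAP section 2 makes the 3205 SAP, whose models all carry polyp status, the default reference unless otherwise indicated. Taking over the primary-model terms also cannot be meant literally for one count per subject, because week effects do not apply. All of this stands, so a reader who concludes that the final pooled models do omit polyp status goes beyond the documents. It does not remove the point: 9.5 gives a model description without the term, and the SAP declares no deviation from Amendment 4. An ISE SAP that followed 9.5 would omit polyp status, and one that followed the 3205 SAP would include it.

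A reader might also infer that SAP 5.1 strips polyp status from the pooled models. Its stated reason fits 3206 data alone, and the next section treats the pooled endpoints separately, so that is not the natural reading.

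Finally, the harm rests on assumed inputs and may be nil. That is correct. Protocol 1.1 cites surgical revision rates of 21% with polyps and 16% without, but this says nothing about exacerbation rates or CSNS change.

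**Conclusion.** The point holds as a minor one. The protocol text for pooled exacerbation frequency (steps 1 and 10) and pooled CSNS (steps 3 and 12) lacks a 3205 stratification factor, and 9.6 lacks the study term that 9.5 gives its own pooled models. Whether the final models will lack them is unknown without the ISE SAP.

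The loss is nil if polyps are not prognostic. For the negative binomial model it is about 0.4-1% in standard error at polyp rate ratios of 1.5-2 and about 3% at a ratio of 3, or roughly 0-3 power points. For CSNS it is under one power point for a 0.5-point polyp difference and reaches 4-5 points only at 1.5 points, a value the documents do not support.

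It would be wrong to read this as a threat to validity. The tests would be at most slightly conservative, and the treatment estimates are not biased by the omission. The co-primary models are unaffected, as are the pooled no-polyp exacerbation tests. Pooled SNOT-22 and PSQI lie outside the testing hierarchy, and polyp status matters there only if subjects with polyps are included.

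**What to change.** State in Protocol 9.5 and SAP 5.2, and carry into the ISE SAP before treatment codes are opened:

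- *Pooled analyses that include subjects with polyps adjust for study (3205, 3206), baseline nasal polyp status (absent, present), previous sinus surgery and, where the endpoint has one, its baseline value.*
- *Pooled analyses restricted to subjects without polyps adjust for study, previous sinus surgery and, where the endpoint has one, its baseline value.*

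In Protocol 9.6, add the study term to the pooled SNOT-22 and PSQI models. Reconcile their population between Protocol 2.3 and 9.6 (no restriction) and 3.2.1.3 (CRS without polyps). Add the polyp term there only if subjects with polyps are included.

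Optionally, say in SAP 5.1 that the removal of polyp status covers only analyses of 3206 alone and pooled no-polyp analyses.

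The cost is a few sentences and one model degree of freedom per added term. No new data are needed, since 3205 recorded polyp status in order to randomise.

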9.6 Other Secondary Efficacy Analyses

All statistical analyses in this section that reference the primary MMRM and ANCOVA models described in Section 9.3.4 will include the same factors as their respective primary models, except for the baseline covariate. The baseline covariate for the specific endpoint will be used, unless otherwise specified.

In addition, a combined dose group (OPN-375 186 µg, OPN-375 372 µg) is defined in all models of primary and secondary endpoints by including appropriate model contrasts, assigning equal weight to each dose, to obtain the inferential statistics for combined doses, and for the comparison: combined dose versus placebo.

Intercurrent events for secondary endpoints will be addressed as described in Section 9.3.3 for the primary estimand, unless otherwise indicated, and poor scores assigned to secondary endpoints are defined in the SAP. For the treatment policy estimand, missing data due to study discontinuation will be handled as described in Section 9.3.4 for the primary MMRM and ANCOVA models, respectively.

The following secondary endpoints will be analyzed with MMRM models; further details will be provided in the SAP:

- Change from baseline in average instantaneous and reflective AM and PM CSNS and symptom scores (facial pain or pressure sensation, nasal discharge, sense of smell, and nasal congestion) – (except AM, instantaneous symptom scores – key secondary endpoints)
- Change from baseline SNOT-22 total scores and sub-domain scores
- Change from baseline to Week 24/ET in SNOT-22 total score in subjects from pooling studies OPN-FLU-CS-3205 and OPN-FLU-CS-3206 who report using an intranasal, topically acting nasal steroid for the treatment of CRS within 30 days of Visit 1
- Change from baseline to Week 24/ET PSQI global and component scores
- Change from baseline to Week 24/ET the Global PSQI Score from pooling studies OPN-FLU-CS-3205 and OPN-FLU-CS-3206
- Change from baseline to Week 4, 8, 12, and 24/ET in HPQ endpoints
 - number and percentage of missing work days over the past 4 weeks
 - percentage of productive work hours lost over the past 4 weeks

The following secondary endpoints will be analyzed using an ANCOVA model; further details will be provided in the SAP. Change from baseline to Week 24/ET:

- Lund-Mackay Staging System total score, scores for ethmoids and maxillary sinuses combined, and scores for each sinus pair (e.g., ethmoids, maxillary, frontal, sphenoid, and ostiomeatal complex),
- WPOV-E, WPOV-M, WPOV
- Zinreich modification of the Lund-Mackay Staging System total score, scores for ethmoids and maxillary sinuses combined, and for each sinus pair (e.g., ethmoids, maxillary, frontal, and sphenoid)
- Zinreich modification of the Lund-Mackay Staging System score for the worst sinus between maxillary and ethmoid sinuses
- percent of opacification of the combined volume of the ethmoid and maxillary sinuses
- SF36v2 MCS Domain, PCS Domain, and individual health domains
- QIDS total score
- SIT scores

Change from baseline to Week 24/ET for EQ-5D VAS scores will be analyzed with the ANCOVA model described above; EQ-5D dimensions will be summarized. Further details will be provided in the SAP.

The percent of subjects considered improved (ie, subjects with ratings of 1 [very much improved] or 2 [much improved]) based on the PGIC at weeks 4 and 24/ET will be analyzed with a logistic regression MMRM model; further details will be provided in the SAP.

The following endpoints will be analyzed using a logistic regression model; further details will be provided in the SAP:

- QIDS Severity of Depression at Week 24/ET
- The percentage of subjects who meet the eligibility criteria for surgery at Week 24

The percent of subjects indicating that they are willing to consider sinus surgery at baseline and Week 24, and the percent of subjects approved for surgery who no longer elect to undergo a surgery Week 24 within each treatment group will be compared with McNemar's test.

Change from baseline to Week 24/ET for SF-6D will be summarized as described in the SAP.

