2.3 Other Secondary Objectives

Secondary objectives of this study are to compare the effect of twice daily doses of 186 and 372 µg of OPN-375 with placebo in:

- change from baseline to Week 24/ET in subject symptoms and functioning, as measured by Sinonasal Outcome Test-22 (SNOT-22) total score for the total population and in patients with and without previous sinus surgery
- change from baseline to Weeks 4, 8, 12, and 24/ET in subject symptoms and functioning, as measured by SNOT-22 total and sub-domain scores for the total population and in patients with and without previous sinus surgery
- change from baseline in symptoms as measured by a CSNS: congestion, facial pain or pressure sensation, and nasal discharge (anterior and/or posterior) to the end of Week 4, 8, and 12 for the total population and in patients with and without previous sinus surgery
- change from baseline to Week 4, 8, and 12 for the total population and patients with and without previous sinus surgery, on facial pain or pressure sensation, nasal discharge (anterior and/or posterior), nasal congestion, and sense of smell as measured by average AM instantaneous symptom scores and PM reflective symptom scores
- change from baseline to Week 24/ET in the APOV in the ethmoid and maxillary sinuses for patients with and without previous sinus surgery
- change from baseline to Week 24/ET in the percent of opacification of the combined volume of the ethmoid and maxillary sinuses
- change from baseline to Week 24/ET in the Lund-Mackay Staging System total score, scores for the maxillary and ethmoid sinuses, and scores for each sinus pair
- change from baseline to Week 24/ET in percent of sinus volume occupied by disease for the worst maxillary sinus (WPOV-M), for the worst ethmoid sinus (WPOV-E), and for the worst sinus between the maxillary and ethmoid sinuses (WPOV) for the total population and in patients with and without previous sinus surgery
- change from baseline to Week 24/ET in the Zinreich modification of Lund-Mackay Staging System total score, scores for the maxillary and ethmoid sinuses combined, and scores for each sinus pair
- change from baseline to Week 24/ET in Zinreich modification of the Lund Mackay Staging System score for the worst sinus between maxillary and ethmoid sinuses in the total population and in subjects with and without previous sinus surgery
- change in patient-reported outcomes from baseline to Week 24/ET as measured by:

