 - change in sleep quality from baseline to Weeks 12 and 24/ET, using the PSQI
 - percent of subjects improved as indicated in the Patient Global Impact of Change (PGIC) at Week 4 and Week 24/ET
 - SF-36v2, 8 individual, physically and emotionally based domains (physical functioning, role-physical, bodily pain, general health, vitality, social functioning, role-emotional, and mental health) standardized scores
 - change in the severity of depression from baseline to Week 24/ET and severity of depression at Week 24/ET as measured by the Quick Inventory of Depression Symptomatology (QIDS)
 - change in severity of olfactory symptoms from baseline to Week 24/ET as measured by the Smell Identification Test (SIT)

- EuroQol-5 (EQ-5D)
- Short Form-6 dimension (SF-6D) derived scores from the SF-36v2
- assessment of health economic measures during the double-blind treatment phase related to CRS (eg, criteria for surgical intervention for CRS is met [independent of actual surgery performed], subjects who entered the study approved for surgery [with a scheduled surgery date] who no longer elect to undergo surgery, missed work or school days/lost productivity) by Health and Work Performance Questionnaire (HPQ)

The following secondary objectives will compare the efficacy of twice daily doses of 186 and 372 µg of OPN-375 with placebo by pooling the data from studies OPN-FLU-CS-3206 and OPN-FLU-CS-3205, which is a separate study being conducted in parallel to this study.

- change from baseline to Week 24/ET in subject symptoms and functioning, as measured by Sinonasal Outcome Test-22 (SNOT-22) total score in subjects who report using an intranasal, topically acting nasal steroid for the treatment of CRS within 30 days of Visit 1
- change in sleep quality from baseline to Week 24/ET, using the Global Pittsburgh Sleep Quality Index (PSQI) Score

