- percent of subjects indicating improvement on the PGIC at Week 4 and Week 24/ET
- severity of depression at Week 24/ET as measured by QIDS
- change from baseline to Week 24/ET for:

- the MCS of the SF36v2
- the PCS of the SF36v2
- SF-36v2 individual domains
- QIDS total score
- SIT scores
- EQ-5D VAS and dimensions
- SF-6D derived scores
- comparison of health economic measures during the double-blind treatment phase related to CRS:
 - percent of subjects indicating that they are willing to consider sinus surgery at baseline and Week 24/ET
 - percent of subjects who meet the minimal objective criteria for surgical intervention (as defined in [Section 7.3](#)) at baseline and Week 24/ET
 - percent of subjects approved for surgery who no longer elect to undergo a surgery Week 24/ET
 - number and percentage of missed work days and the percentage of productive hours lost while at work from the HPQ
- change from baseline to Week 24/ET in SNOT-22 total score in subjects who report using an intranasal, topically acting nasal steroid for the treatment of CRS within 30 days of Visit 1 in subjects with CRS without NP, from studies OPN-FLU-CS-3206 and OPN-FLU-CS-3205 (pooled data)
- change from baseline to Week 24/ET the Global PSQI Score in subjects with CRS without NP, from studies OPN-FLU-CS-3206 and OPN-FLU-CS-3205 (pooled data)

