8. have current evidence of odontogenic sinusitis, sinus mucocele (the affected sinus is completely opacified and either the margins are expanded and/or thinned OR there are areas of complete bone resorption resulting in bony defect and extension of the “mass” into adjacent tissues), evidence of allergic fungal sinusitis, or evidence of complicated sinus disease (including, but not limited to, extension of inflammation outside of the sinuses and nasal cavity)
9. have a paranasal sinus or nasal tumor
10. have polyp grade ≥ 1 (polyp that is free on 5 sides and has a stalk) on either side of the nose as determined by the nasoendoscopy at screening
11. have a nasal septum perforation
12. have had more than 1 episode of epistaxis with frank bleeding in the month before Visit 1 (Screening)

13. have evidence of significant mucosal injury, ulceration (eg, exposed cartilage) on Visit 1 (Screening) nasal examination/nasoendoscopy
14. have current, ongoing rhinitis medicamentosa (rebound rhinitis)
15. have significant oral structural abnormalities (eg, a cleft palate)
16. have a diagnosis of cystic fibrosis
17. history of eosinophilic granulomatosis with polyangiitis (Churg–Strauss syndrome) or dyskinetic ciliary syndromes
18. symptom resolution or last dose of antibiotics for purulent nasal infection, acute sinusitis, upper respiratory tract infection, influenza, or SARS-CoV-2 (COVID-19) has not occurred before Visit 1 or was less than 4 weeks before the CT scan. Potential subjects presenting with any of these infections may be rescreened 4 weeks after symptom resolution
19. planned sinonasal surgery during the period of the study
20. allergy, hypersensitivity, or contraindication to corticosteroids or steroids
21. has used oral steroids in the past for treatment of CRS and did not experience any relief of symptoms
22. has a steroid eluting sinus stent still in place within 30 days of Visit 1
23. allergy or hypersensitivity to any excipients in study drug
24. exposure to any glucocorticoid treatment with potential for systemic effects (eg, oral, parenteral, intra-articular, or epidural steroids, high dose topical steroids) within 1 month before Visit 1 (Screening); except as noted in inclusion criteria for subjects with comorbid asthma or COPD
25. have nasal candidiasis
26. history or current diagnosis of any form of glaucoma or ocular hypertension
27. history of IOP elevation on any form of steroid therapy

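### For two surgery endpoints, Protocol 9.6 names only a within-arm McNemar's test, although the secondary objective is each dose versus placebo

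*Protocol*

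**What the plan says.** Section 2.3 of the protocol opens its list with "Secondary objectives of this study are to compare the effect of twice daily doses of" 186 and 372 µg with placebo. Under that opening it lists health economic measures, with the example "subjects who entered the study approved for surgery [with a scheduled surgery date] who no longer elect to undergo surgery".

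Section 3.2.1.3 heads the matching endpoints "comparison of health economic measures during the double-blind treatment phase related to CRS". Two of them matter here:

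- (a) "percent of subjects indicating that they are willing to consider sinus surgery at baseline and Week 24/ET";
- (b) the percentage of subjects approved for surgery who no longer want it at Week 24/ET.

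Section 9.6 handles (a) and (b) in one sentence, which ends with subjects "who no longer elect to undergo a surgery Week 24 within each treatment group will be compared with" McNemar's test. A third surgery endpoint is listed for logistic regression: "The percentage of subjects who meet the eligibility criteria for surgery at Week 24".

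Section 9.6 also has a general rule that provides "inferential statistics for combined doses, and for the comparison: combined dose versus placebo", but it does so through contrasts in models.

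The SAP does not mention (a) or (b). Its Section 2 declares no deviations from the protocol and makes the CS-3205 SAP the primary reference for methods. Its Section 5.1 removes the polyp term from the models and says nothing else changes.

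**The concern.** The objective asks whether each dose differs from placebo. The named test asks whether responses changed between baseline and Week 24 among subjects in the same arm. In a trial with a placebo run-in, repeated contact and symptom-based entry criteria, attitudes to surgery can shift in every arm, placebo included. A within-arm test cannot separate that shift from a drug effect.

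If the within-arm results are all that is produced, the stated objective goes unanswered for these endpoints, or a between-arm test is chosen after unblinding. If p-values from separate arms were set side by side and read as a treatment comparison, which no passage proposes, they could mislead in either direction.

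**Working it through.** **Inputs.** The plan gives no power, switch rate or count of approved subjects for either endpoint, so there is no stated figure to reproduce. Protocol 9.1 gives 70 subjects per arm. Every switch rate and every count of approved subjects below is an assumption. Tests are two-sided at 0.05.

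**Does anything in the supplied text supply a between-arm test?**

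- The 9.6 sentence is loosely punctuated, and the within-group phrase could attach to (b) alone. McNemar's test is paired on either reading.
- The combined-dose rule works through model contrasts. A within-arm McNemar's test has no treatment term to contrast.
- The SAP is silent on both endpoints.

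So none is named.

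**Endpoint (b): no longer electing surgery.** Section 2.3 defines the group as subjects approved on entry. All start in the same state, so change can go one way only. Let *b* be the number in an arm who changed their mind.

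- Exact version: p = 2 × 0.5^*b*.
- Uncorrected version: chi-square = (*b* − 0)² / (*b* + 0) = *b*, on 1 degree of freedom.

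| *b* | Exact p | Uncorrected p |
|---|---|---|
| 3 | 0.25 | 0.083 |
| 4 | 0.125 | 0.046 |
| 5 | 0.0625 | 0.025 |
| 6 | 0.031 | 0.014 |

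Neither the number approved nor the placebo result enters the formula. Illustrations:

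| Arm 1 | Arm 2 | McNemar p within each arm | Fisher p between arms |
|---|---|---|---|
| 6 of 10 | 5 of 10 | 0.031 and 0.0625 (exact) | 1.00 |
| 4 of 10 | 3 of 10 | 0.046 and 0.083 (uncorrected) | 1.00 |
| 6 of 8 | 6 of 20 | 0.031 and 0.031 (exact) | 0.044 |

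The first two rows split arms that barely differ. The third gives identical results for arms at 75% and 30%. An arm with fewer than 6 approved subjects (exact) or fewer than 4 (uncorrected) cannot reach 0.05. The group may be small, because exclusion 19 in Section 4.2 bars "planned sinonasal surgery during the period of the study".

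**Endpoint (a): willingness.** Assume no treatment effect, so both arms have the same switch rates, and 70 complete pairs per arm. Let *p* be the probability that one arm's exact McNemar's test is significant, found by enumerating all outcomes. The arms are independent, so the probability that a given active arm is significant and placebo is not is *p*(1 − *p*). The probability that exactly one of the two is significant is 2*p*(1 − *p*).

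| To unwilling / to willing | *p* | Active only | Exactly one |
|---|---|---|---|
| 20% / 5% | 0.668 | 0.222 | 0.444 |
| 20% / 8% | 0.398 | 0.240 | 0.479 |
| 20% / 10% | 0.258 | 0.191 | 0.383 |
| 25% / 5% | 0.863 | 0.118 | 0.236 |
| 25% / 8% | 0.647 | 0.228 | 0.457 |
| 25% / 10% | 0.492 | 0.250 | 0.500 |
| 30% / 5% | 0.955 | 0.043 | 0.086 |
| 30% / 8% | 0.832 | 0.140 | 0.279 |
| 30% / 10% | 0.713 | 0.205 | 0.409 |
| 10% / 10% | 0.026 | 0.026 | 0.052 |

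Variations over the first nine rows:

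- Uncorrected version: active only 0.025 to 0.250; exactly one 0.049 to 0.500.
- Exact version with 20% missing (70 × 0.8 = 56 pairs): active only 0.092 to 0.249; exactly one 0.184 to 0.497.

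With no net change (10% / 10%), active only is about 3% (exact) or 4% (uncorrected). The problem therefore appears when both arms shift.

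**The case against.** **The governing methods document is missing.** The CS-3205 SAP is the primary reference, and the supplied SAP covers only changes and additions, so its silence is expected. This stands. Absence is shown only for the protocol and the CS-3206 SAP. Even if the CS-3205 SAP has a between-arm test, 9.6 itself names only a within-arm one.

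**For (a) the objective is only implied.** Willingness is not among the examples in Section 2.3, and comparison in 3.2.1.3 could mean baseline against Week 24. This partly stands: McNemar's test is a proper analysis of within-arm change in (a). But the opening of 2.3 covers all the health economic measures, so dose versus placebo remains the natural reading. For (b) the listing is explicit.

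**Some lower-tier endpoints are deliberately only summarised.** The EQ-5D dimensions and SF-6D get no test in 9.6. That is a legitimate choice, but here a test is named, and it answers a different question from the objective.

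**The one-way change in (b) is an inference.** The protocol does not set out the paired table. The inference follows from the wording of 2.3, but a different coding in the CS-3205 SAP would change the p-values shown.

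**The percentages are illustrations.** They rest on assumed rates, and *p*(1 − *p*) and 2*p*(1 − *p*) can never exceed 25% and 50%. They measure a misreading that the plan does not propose. This stands, and they should be read that way. Arm-level percentages will also be available, so a reader could see the between-arm differences directly.

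**Conclusion.** The point holds and is minor. On the supplied documents, the only test named for these two endpoints does not address dose versus placebo. For (b) it also ignores both the denominator and the placebo arm.

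The mismatch follows from the text and from the paired nature of the test. Its possible size rests on assumed switch rates and invented counts, and the figures for (b) also assume that every counted subject was approved at entry.

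Both endpoints are outside the testing hierarchy, so the primary and key secondary conclusions are unaffected. The main uncertainty is the content of the CS-3205 SAP.

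**What to change.** First check whether the CS-3205 SAP already gives a between-arm analysis for these endpoints. If it does, cite it in 9.6. If not, add the following to 9.6 or to the SAP before unblinding:

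- **(a) Willingness:** logistic regression of the Week 24 response on treatment, previous sinus surgery and baseline willingness, reporting each dose against placebo. Section 9.6 already uses logistic regression for the surgical-criteria endpoint; the covariate set is a proposal.
- **(b) No longer electing surgery:** an exact test of the proportion among subjects approved at entry, each dose against placebo, or counts only if the group is very small.
- Keep within-arm change as descriptive and, if McNemar's test is retained, name the version.
- State how missing Week 24 responses and surgery actually performed during the study are handled, since both bear directly on these endpoints.

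The cost is a short protocol amendment, or a deviation declared in the SAP. No new data are needed: the surgical intervention assessment is already scheduled at Visits 2 and 6.
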